### 7.4.2 Prior and Concomitant Medications

Refer to Section 7.4.2 of the Core SAP for VTE Prevention.

## 7.5 Efficacy

The event rates and their 95% confidence intervals of composite of venous thromboembolism (VTE) and all cause death based on efficacy population will be summarized. Subgroup summary by surgery type (knee or hip) will also be conducted.

## 7.6 Safety

Bleeding is the primary safety outcome measure. The event rate of adjudicated major bleeding or clinically relevant non-major bleeding events during the treatment period will be summarized. Subgroup summary for bleeding by surgery type (knee or hip) will also be conducted.

The incidence of adverse events will be summarized for both the treatment and follow-up period by surgery type (knee or hip). Any post-dose marked abnormalities in clinical laboratory tests will be listed.

All adverse events that are serious or that result in discontinuation of study therapy will be described in depth.

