Total of 500 subjects will be enrolled and allocated to apixaban. The sample size of the study is determined by requirement of regulatory agency rather than statistical considerations. With 500 subjects and event rate of 4.36% for ISTH major or clinically relevant non-major bleeding, the width of the 95% CI for the event rate will be (2.6%, 6.2%) and width of the CI is 3.6%.

Subgroup analyses by surgery type will also be conducted.

TABLE OF CONTENTS

TITLE PAGE	1
DOCUMENT HISTORY	3
SYNOPSIS.....	4
TABLE OF CONTENTS.....	7
1 [REDACTED].....	9
[REDACTED].....	9
[REDACTED].....	9
[REDACTED].....	9
[REDACTED].....	10
[REDACTED].....	10
2 ETHICAL CONSIDERATIONS.....	10
2.1 Good Clinical Practice	10
2.2 Institutional Review Board/Independent Ethics Committee.....	10
2.3 Informed Consent.....	11
3 INVESTIGATIONAL PLAN.....	12
3.1 Study Design and Duration.....	12
3.1.1 Screening.....	13
3.1.2 Enrollment.....	13
3.1.3 Treatment Period.....	13
3.1.4 Follow-up Period.....	14
3.2 Post Study Access to Therapy.....	14
3.3 Study Population.....	14
3.3.1 Inclusion Criteria.....	14
3.3.2 Exclusion Criteria.....	15
3.3.3 Women of Childbearing Potential	16
3.4 Concomitant Treatments.....	17
3.4.1 Prohibited and/or Restricted Treatments.....	17
3.4.2 Other Restrictions and Precautions.....	17
4 TREATMENTS	19
4.1 Study Treatments	20
4.1.1 Investigational Product.....	21
4.1.2 Noninvestigational Product	21
4.1.3 Handling and Dispensing	21
4.2 Method of Assigning Subject Identification	21
4.3 Selection and Timing of Dose for Each Subject.....	22
4.4 Blinding/Unblinding	22
4.5 Treatment Compliance.....	22
4.6 Destruction and Return of Study Drug	22
4.6.1 Destruction of Study Drug	22
4.6.2 Return of Study Drug	22
5 STUDY ASSESSMENTS AND PROCEDURES.....	23
5.1 Flow Chart/Time and Events Schedule.....	23
5.2 Study Materials	27
5.3 Safety Assessments.....	27

5.4 Efficacy Assessments.....	28
5.4.1 Primary Efficacy Assessment.....	29
5.4.2 Secondary Efficacy Assessments.....	29
[REDACTED].....	29
6 ADVERSE EVENTS.....	29
6.1 Serious Adverse Events	29
6.1.1 Serious Adverse Event Collection and Reporting.....	30
6.2 Nonserious Adverse Events	31
6.2.1 Nonserious Adverse Event Collection and Reporting.....	31
6.3 Laboratory Test Abnormalities.....	31
6.4 Pregnancy.....	32
6.5 Overdose	32
6.6 Potential Drug Induced Liver Injury (DILI).....	32
6.7 Other Safety Considerations	33
7 DATA MONITORING COMMITTEE AND OTHER EXTERNAL COMMITTEES	33
7.1 Data Monitoring Committee.....	33

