3.1.2 Enrollment

The enrollment may occur from 4 days prior to surgery to 24 hours after surgery.

Subjects who meet all the inclusion/exclusion criteria will be enrolled to the site for this visit. Subjects (N = 500) will be assigned to oral apixaban 2.5 mg BID

Blood sample and Urine pregnancy test will be collected for laboratory assessments.

Sites will call into the IVRS system for assignment to apixaban 2.5 mg; sites will indicate whether the subject is undergoing either a TKR or THR. Either hip or knee replacement patients may be enrolled in any order, but BMS may place enrollment limits on either type of surgical patient to ensure adequate enrollment of both knee and hip surgery patients in the study.

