8.4.2 Efficacy Analyses

The event rates and their 95% confidence intervals of composite of venous thromboembolism (VTE) and all cause death during the treatment period will be summarized. Subgroup analyses by surgery type will also be conducted.

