### **7.1 General Methods**

Refer to Section 7.1 of the Core SAP for VTE Prevention for further details on statistical methods.

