### 7.6.1 Adverse Events

Refer to Section 7.6.2.1 in the Core SAP for VTE Prevention.

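### Does the primary bleeding analysis need a stated confidence interval, and the SAP's acceptability wording a criterion, before the plan can be followed?

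*SAP*

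**What the plan says.** SAP 7.6 and Protocol 8.4.3 describe the primary analysis in the same terms: "The event rate of adjudicated major bleeding or clinically relevant non-major bleeding events during the treatment period will be summarized". SAP 7.6 adds "Subgroup summary for bleeding by surgery type (knee or hip) will also be conducted". Neither section names an interval.

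The secondary endpoint is treated differently. Protocol 8.4.2 plans "The event rates and their 95% confidence intervals of composite of venous thromboembolism (VTE) and all cause death during the treatment period", and SAP 7.5 likewise plans "The event rates and their 95% confidence intervals of composite of venous thromboembolism (VTE) and all cause death".

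The sample-size text (Protocol Synopsis and 8.1, SAP 5) says the regulator set the number of subjects. It then gives the study's only precision statement, for 500 subjects and a bleeding rate of 4.36%: "the width of the 95% CI for the event rate will be (2.6%, 6.2%) and width of the CI is 3.6" (per cent).

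The SAP is written as a supplement. Section 7.1 says "Refer to Section 7.1 of the Core SAP for VTE Prevention for further details on statistical methods", and the subsections under 7.6 do the same, for example 7.6.1: "Refer to Section 7.6.2.1 in the Core SAP for VTE Prevention". Section 9 defers report content to that document too.

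SAP 1.1, 3.1 and 3.2 state the hypothesis and objectives in terms of an acceptable rate of bleeding, or of VTE and death. The Protocol Synopsis uses other words: its hypothesis is that apixaban is well tolerated, and its objective is to evaluate safety.

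**The concern.** In a single-arm study with no test, the estimate and its interval are the primary result. Here the supplied text gives an interval to the secondary endpoint and none to the primary one, although the sample size is described by exactly that interval. No method is named anywhere, including for the VTE and death composite.

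Two things could be at stake. The bleeding rate might be reported as a bare percentage, above all by surgery type, where it is less precise than the pooled 3.6 points. And with no threshold for an acceptable rate, any observed rate could be called acceptable afterwards.

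**Working it through.** **Inputs.** n = 500 and p = 4.36% (Protocol 8.1, SAP 5), so 500 × 0.0436 = 21.8 expected events. The printed interval is 2.6% to 6.2%, width 3.6 points. No knee/hip split is given, so group sizes below are assumptions.

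**Step 1: reproduce the plan's figure.** Wald interval: p ± 1.96 × √(p(1 − p)/n).

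- At p = 0.0436: √(0.0436 × 0.9564/500) = 0.00913, and 1.96 × 0.00913 = 0.0179. Limits 2.57% to 6.15%, width 3.58 points.
- At the nearest whole count, 22/500 = 4.4%: 2.60% to 6.20%, width 3.60 points. This matches the printed figures.

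The planning interval is sound, and it shows what kind of summary the authors had in mind for bleeding.

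**Step 2: does the unnamed method matter for the pooled result?** At 22/500:

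| Method | 95% interval | Width (points) |
|---|---|---|
| Wald | 2.60% to 6.20% | 3.60 |
| Wilson | 2.92% to 6.57% | 3.65 |
| Clopper-Pearson | 2.78% to 6.59% | 3.81 |

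The largest shift from Wald is 2.92 − 2.60 = 0.32 points at the lower limit and 6.59 − 6.20 = 0.39 points at the upper. No threshold sits nearby for such a shift to cross.

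**Step 3: by surgery type.** Wald width scales with 1/√n, so at 250 per group it is 3.58 × √(500/250) = 5.06 points. Over a range of assumed sizes, with Wald taken at 4.36% and Clopper-Pearson at the nearest whole count:

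| Assumed group size | Nearest count | Wald at 4.36% | Clopper-Pearson at count |
|---|---|---|---|
| 150 | 7 | 1.09% to 7.63% | 1.90% to 9.38% |
| 200 | 9 | 1.53% to 7.19% | 2.08% to 8.37% |
| 250 | 11 | 1.83% to 6.89% | 2.22% to 7.74% |
| 300 | 13 | 2.05% to 6.67% | 2.33% to 7.30% |
| 350 | 15 | 2.22% to 6.50% | 2.42% to 6.97% |

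At 11/250 Wilson gives 2.47% to 7.71%, close to Clopper-Pearson. Very small groups would be less precise still, but Protocol 3.1.2 makes them less likely. It says "BMS may place enrollment limits on either type of surgical patient", and the same sentence gives the purpose as securing enough patients of both kinds. Neither document claims any precision for the subgroups, so no stated figure is contradicted.

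**Step 4: what depends on the interval or on acceptability?** The documents give no null rate, margin, alpha, power or stopping rule, and they plan no interim analysis. The sample size was set by the regulator. An analyst following SAP 7.6 literally reports the correct rate in the treated population, and the interval follows from the numerator and denominator.

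**Step 5: the acceptability wording beside the protocol.** The protocol counterpart of SAP 1.1 is the hypothesis of good tolerability, which also has no criterion. SAP 3.2 concerns VTE and death, for which the protocol's safety objective is no counterpart. Rewriting these lines as estimation would move SAP 1.1 away from the protocol's hypothesis and would change no analysis. Protocol Section 1 is redacted and the title of SAP Section 1 is blank. A reference rate, or the source of the 4.36%, may stand there.

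**The case for a change.** The best case for a change is the asymmetry. SAP 7.5 states its interval locally although the pointer in 7.1 covers it too, so the silence in 7.6 cannot be put down wholly to the Core SAP. The bleeding paragraph of 7.6 cites no Core SAP section. Stating the interval would take one sentence in the SAP, with no protocol revision.

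Method can also matter if events turn out far fewer than planned. At 3/500, Wald (cut off at zero) gives 0% to 1.28%, Wilson 0.20% to 1.75% and Clopper-Pearson 0.12% to 1.74%. The undefined acceptable rate also leaves room for a favourable reading after the fact.

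Most of this is true as description. The asymmetry is real, and a sentence would be tidy. But it would only write down what the sample-size text already shows to be intended. The few-events case is well below the plan's own 21.8 expected events, and even there no decision turns on the method. The looseness of an acceptable rate is a matter for how the report words its conclusion: without a criterion, the rate and its interval speak for themselves. That no criterion exists cannot be concluded while background text is redacted and the Core SAP is unseen.

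**Conclusion.** No change to the plan follows. The interval's absence from SAP 7.6 and Protocol 8.4.3 is missing detail that any analyst would fill from the sample-size text and the parallel sections on VTE and death. Following the plan as written gives no wrong result. At the planned rate the choice of method moves the pooled limits by at most 0.4 points. The by-surgery intervals are wider, about 5.1 points (Wald) at an assumed 250 per group, but the plan promises nothing narrower. The acceptability wording is loose, no looser than the protocol's own hypothesis, and drives no analysis.

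This rests on three assumptions: the event rate is near 4.36%, neither surgery group is very small, and the report gives the counts with their denominators, so that the interval can be checked whatever the Core SAP says.

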### 7.6.1 Adverse Events

Refer to Section 7.6.2.1 in the Core SAP for VTE Prevention.

### **7.6.2 Laboratory Data**

Refer to Section 7.6.2.2 in the Core SAP for VTE Prevention. Hemoglobin is the parameter which will be summarized.

### **7.6.3 Events of Special Interest**

Refer to Section 7.6.2.4 in the Core SAP for VTE Prevention.

## **8 CONVENTIONS**

### **8.1 Safety Data Conventions**

Refer to Section 8.1 of the Core SAP for VTE Prevention.

### **8.2 Baseline Measurements**

Refer to Section 8.2 of the Core SAP for VTE Prevention.

### **8.3 Day Ranges for Analysis of Time Points**

Subjects do not always adhere strictly to the visit schedule timing in the protocol. The day ranges for the summary of laboratory measurements are defined in the following tables.

**Table 8.3A: Day Ranges for summary of Laboratory Measurements**

Nominal Visit	Target Day	Day Ranges
Screening	Pre-Surgery 1-14 day	Screening to < Enrollment
Enrollment	Pre-Surgery -4 day - 24 hours	Enrollment to < start of surgery
Hospital discharge	Hospital discharge	Day 2 to < End of treatment period

### **8.4 Multiple Measurements**

Refer to Section 8.4 of the Core SAP for VTE Prevention.

## **9 CONTENT OF REPORTS**

Refer to Section 9 of the Core SAP for VTE Prevention.

## **APPENDIX 1      ANALYSIS OF SAFETY DATA - REFERENCE TO CT SOP 109**

The original GD SOP 12 in Core SAP is retired and replaced by CT SOP 109.

